Hypothesis	
In Part 2, the overall response rate (p) of GCB-DLBCL and tFL patients will be assessed for each EZH2 mutation status cohort (wild type and mutant), and also for MM patients.
 
 • For each of the GCB-DLBCL and tFL cohort, the null and alternative hypotheses of the overall response rate are as following: 
The null hypothesis is:
 
$H_0: p \leq 20\%$
 
The alternative hypothesis is:
 
$H_A: p \geq 40\%$
 
 • For MM cohort: 
The null hypothesis is:
 
$H_0: p \leq 10\%$
 
The alternative hypothesis is:
 
$H_A: p \geq 25\%$
 
The primary objective of Part 2 is to determine whether administration of GSK2816126 has a potentially clinically meaningful response rate.
 
 • In subjects with GCB-DLBCL, this will be determined in each EZH2 mutation status cohort (wild type and mutant) by testing the null hypothesis that the response rate is $\leq 10\%$, with about 90% power when the true response rate is 30%. • In subjects with tFL, this will be determined in each EZH2 mutation status cohort by testing the null hypothesis that the response rate is $\leq 5\%$, with about 80% power when the true response rate is 25%. • In subjects with MM, this will be determined by testing the null hypothesis that the response rate is $\leq 5\%$, with about 85% power when the true response rate is 20%. 	

Section 3.1 Study Schematic

Rationale for Change: Updated study schematic to include Part 1 expansion cohort.

REVISED TEXT

Part 1
Accelerated Dose Titration followed by 3+3 Dose Escalation

To determine the safety and tolerability of GSK2816126 in subjects with relapsed/refractory DLBCL, transformed FL, other NHLs, solid tumors and MM

Part 1 will include a cohort expansion at MTD or any dose level to enroll subjects with GCB-DLBCL and solid tumors with EZH2 inhibitor sensitizing mutations or prostate cancer

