6.3. Permanent Discontinuation from Study Treatment

Subjects will receive study treatment until disease progression, death or unacceptable toxicity, including meeting stopping criteria for liver chemistry defined in Section 8.3.1. In addition, study treatment willmay be permanently discontinued for any of the following reasons:

- Substantial deviation(s) from the protocol
- Request of the subject or proxy (withdrawal of consent by subject or proxy)
- Investigator's discretion

- A dose delay of > 21 days unless the investigator and GSK Medical Monitor agree that further treatment may benefit the subject
- Intercurrent illness that prevents further administration of study treatment(s)
- Subject is lost to follow-up or study is closed or terminated.

The primary reason study treatment was permanently discontinued must be documented in the subject's medical records and eCRF.

If the subject voluntarily discontinues from treatment due to toxicity, 'adverse event' will be recorded as the primary reason for permanently discontinuation on the eCRF.

Once a subject has permanently discontinued from study treatment, the subject will not be allowed to be retreated.

~~If the subject voluntarily discontinues from treatment due to toxicity, 'AE' will be recorded as the primary reason for permanently discontinuation on the eCRF.~~

Section 7: STUDY ASSESSMENTS AND PROCEDURES

Table 6 Time and Events, Treatment Phase: Screening through Day 28 (See also PK sampling table for PK sampling schedule on Day 1 and Day 15)

Details added:

- Window period of '-1 Day' was added to the Safety Assessments heading under Study Phase column
- 'At Screening' was added under Visit Window for ECHO assessment
- The frequency of assessment was changed from 'Every 4 weeks' to Prior to every infusion' for Hematology parameters in Continuation phase
- Day 4 pre-dose and end of infusion was added for PK sampling for Part 1 at Day 1 and 4 Visit.
- Blood samples for Genetic research were added at screening and Day 1 and 4 Visit.
- The time points for blood samples obtained for assessing PD biomarkers were revised as prior to dosing on D1 (baseline), 2 hours after the end of the infusion on day 1, 4, 8, 11, 15, and 18 and at day 21 and 28 visits (\pm 1-2 days).
- Archival Tissue for mutation testing will be for All DLBCL and tFL subjects.
- The time points for tumor biopsy was revised to be obtained at D1 (up to -14 days) and after 6th dose Day 18 (+3 day window)

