Hepatic Toxicity	
In first in human study EZH117208 (present study), an increase in level of ALT has been noted in the group of subjects receiving doses of 1800 mg to 3000 mg (single infusion dose). None of these ALT increases have been associated with increase in total bilirubin or INR and all have shown improvement following either withholding or discontinuing GSK2816126. The 3000 mg dose has been declared to exceed the MTD. The highest dose being explored in this study is 2400 mg.
 
In nonclinical species given GSK2816126, twice weekly for 2 and/or 4 weeks, changes in liver pathology (inflammation, hyperplasia) in dogs and clinical chemistry parameters (i.e. increases in ALT, AST, ALP, bilirubin and decreases in albumin) in rats and dogs were observed and were
	
Dosing at 3000 mg has been discontinued, with the highest dose being explored is at 2400 mg. Continued laboratory and clinical monitoring for liver dysfunction (LFT, coagulation parameters INR/PTT, other blood chemistry, clinical observation for jaundice). Dose management and stopping criteria as per guidelines for non-hematologic toxicity (Section 3.8.3 and Table 4) and hepatic safety monitoring (Section 8.3.1)

Potential Risk of Clinical Significance	Data/Rationale for Risk	Mitigation Strategy

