G2	Continue dosing with no change OR Consider holding for up to 2 weeks for toxicity to resolve to baseline or \leq Grade 1, then continue at the same dose OR dose reduce by at least 25% to 1 dose level lower per dose escalation scheme if the toxicity is considered a DLT.
G3 and 4	Hold for up to 2 weeks for toxicity to resolve to baseline or \leq Grade 1, then dose reduce by at least 25% to 1 dose level lower per dose escalation scheme If no recovery to \leq Grade 1* or baseline after 14 days, patient should be withdrawn.

If the non-hematologic toxicity or event resolves to baseline or \leq Grade 1 within 14 days of stopping therapy, treatment with GSK2816126 may be restarted at 1 with at least 25% dose level lower than the current dose reduction. For a non-DLT, the treatment with GSK2816126 could restart at a full dose, if deemed appropriate.

If the non-hematologic toxicity does not resolve to \leq Grade 1 or baseline within 14 days, the subject should be withdrawn from the treatment permanently (Section 6.3). However, if the investigator and GSK Medical Monitor agree that further treatment will benefit the subject, treatment can restart with at least 25% dose reduction 1 dose level lower and under weekly clinical monitoring. If the toxicity resolves to \leq Grade 1 or baseline, the dose may be resumed to the initial dose level.

Section 3.8.4.1 For subjects with lymphoma and multiple myeloma:**REVISED TEXT**

When the treatment resumes, the dose may be adjusted based on platelet count, i.e., dose can be reduced by ~~at least 25% increments up to twice 1 or 2 dose levels~~ when the platelet count $\leq 25 \times 10^9/L$ (G4 thrombocytopenia) and it is not attributed to the disease. If a subject has persistent G4 thrombocytopenia for 4 weeks not attributed to disease or requires platelet transfusions for bleeding in the absence of the disease, the subject will be withdrawn from the study.

Section 3.8.4.2 For subjects with solid tumors:**REVISED TEXT**

- Grade 3 (platelet count between 25,000 to $<50,000$): After discussion with medical monitor and using sound clinical judgement, continue at same dose or ~~consider dose interruption until adjust dose (e.g. consider missing one dose or till count recovery to Grade 2 or less). Monitor platelet count CBC at least a minimum of twice a weekly, more frequently if necessary.~~

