- Grade 4 (platelet count below 25,000): Interrupt study medication and monitor ~~CBC platelet count~~ every 2-3 days. If platelet counts recover to Grade 2, discuss with medical monitor resuming treatment at the same or adjusted dose based on sound clinical judgement. Platelet transfusion is allowed based on institutional guidelines. In case of platelet transfusion, hold drug for at least 7 days from day of transfusion, and if platelet counts recover to Grade 2 consider initiating treatment at a lower dose using sound clinical judgement and after consulting with the GSK medical monitor. Discontinue treatment if drug has to be held for >14 days or greater than 2 dose reductions required.

Section 3.9.1 Dose Modifications**REVISED TEXT**

Dose reductions for GSK2816126 will depend on their starting dose. If a subject has a dose reduction for toxicity the dose will be reduced ~~by one dose level by a minimum of 25%~~. Approval from the GSK Medical Monitor is required to restart a dose after 14 days of dose interruption. Following a dose reduction subjects may be re-escalated to a higher dose level with the approval of the GSK Medical Monitor if the toxicity has resolved.

Section 5.1 Number of Subjects

Rationale for Change: updated total number of subjects to be enrolled based on added Part 1 expansion cohorts and revised subject numbers in Part 2.

REVISED TEXT

A maximum of approximately 250~~169~~ subjects will be enrolled. See Section 12.2 for sample size assumptions.

The number of dose levels and the level at which the RP2D (or MTD or MFD) is reached cannot be determined in advance. An adequate number of subjects will be enrolled into the study to establish the recommended dose(s) for further study. It is estimated that approximately 40 subjects will be enrolled into Part 1 dose-escalation of the study.

Additionally i-n Part 1 cohort expansion, approximately 27 GCB-DLBCL subjects and approximately 15 solid tumor subjects containing EZH2 inhibitor sensitizing mutations or subjects with prostate cancer will be enrolled.

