Rationale for Change: The Liver Events section was reorganized with updated tables and figures. Stopping/monitoring criteria for subjects with baseline ALT $\leq 2.5 \times \text{ULN}$ have not changed. Stopping/monitoring criteria rules were further clarified for subjects with documented liver metastases/tumor infiltration at baseline and entry criteria ALT $> 2.5 \times \text{ULN}$ but $< 5 \times \text{ULN}$. Study treatment restart/rechallenge criteria was added. Details moved to Appendix 3.

[figure not shown]
REVISED TEXT

Liver chemistry threshold stopping criteria have been designed to assure subject safety and to evaluate liver event etiology during administration of study treatment(s) and the follow-up period (in alignment with the FDA premarketing clinical liver safety guidance). Study treatment(s) will be stopped if any of the following liver chemistry stopping criteria is/are met:

<http://www.fda.gov/downloads/Drugs/GuidanceComplianceRegulatoryInformation/Guidances/UCM174090.pdf>

[figure not shown]
See Figure 1 and Figure 2 for liver stopping criteria for subjects without and with liver metastases, respectively. The algorithms are best read from left to right.

Figure 1 Phase I/II Liver Chemistry Stopping and Increased Monitoring Algorithm for Subjects WITH entry criteria ALT $\leq 2.5 \times$ ULN

Liver Safety Required Actions and Follow up Assessments Section can be found in Appendix 3

Figure 2 Phase I/II Liver Chemistry Stopping and Increased Monitoring Algorithm including Subjects WITH documented liver metastases/tumor infiltration at baseline AND entry criteria ALT>2.5xULN but \leq 5xULN

Liver Safety Required Actions and Follow up Assessments Section can be found in Appendix 3

Section 8.3.1.1 Study Treatment Restart or Rechallenge

If subject meets liver chemistry stopping criteria do not restart/rechallenge subject with study treatment unless:

- GSK Medical Governance approval is granted
- Ethics and/or Institutional Review Board (IRB) approval is obtained, if required, and
- Separate consent for treatment restart/rechallenge is signed by the subject

Refer to Appendix 3 for full guidance

- ~~ALT \geq 3 times ULN and bilirubin \geq 2 times ULN (or ALT \geq 3 times ULN and INR $>$ 1.5)~~

NOTE: Serum bilirubin fractionation should be performed if testing is available. If fractionation is unavailable, urinary bilirubin is to be measured via dipstick (a measurement of direct bilirubin, which would suggest liver injury).

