Bilirubin^{1, 2}	ALT ≥ 3xULN and bilirubin ≥ 2xULN (>35% direct bilirubin)
INR²	ALT ≥ 3xULN and INR>1.5, if INR measured
Cannot Monitor	Both ALT ≥ 3xULN and ≥ 1.5x baseline value that cannot be monitored for 4 weeks
Symptomatic³	Both ALT ≥ 3xULN and ≥ 1.5x baseline value associated with symptoms (new or worsening) believed to be related to liver injury or hypersensitivity
Required Actions and Follow up Assessments following ANY Liver Stopping Event	
Actions	Follow Up Assessments

 Immediately discontinue study treatment Report the event to GSK within 24 hours Complete the liver event eCRF and complete an SAE data collection tool if the event also meets the criteria for an SAE² 	
 Viral hepatitis serology⁴ Blood sample for pharmacokinetic (PK) analysis, obtained approximately 48h after last dose⁵ Serum creatine phosphokinase (CPK) and lactate dehydrogenase (LDH)

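### After a liver stopping event, Table 4 allows hold-and-restart one dose level lower, while Section 8.3.1.1 and Appendix 3 bar restart without governance approval and new consent; nothing says which rule governs

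*Protocol*

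**What the plan says.** Both rule sets below stand as revised text in Amendment 5.

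- **Section 1.3.1, Hepatic Toxicity row.** ALT rises have been seen at 1800 to 3000 mg, and 2400 mg is still being explored. The mitigation column reads: "Dose management and stopping criteria as per guidelines for non-hematologic toxicity (Section 3.8.3 and Table 4) and hepatic safety monitoring (Section 8.3.1"). No order of precedence is given.
- **Section 3.8.3 and Table 4.** For drug-related Grade 3 and 4 non-hematologic toxicity: "Hold for up to 2 weeks for toxicity to resolve to baseline" or to Grade 1 or lower, then reduce by one dose level. The text below the table permits restart one level lower after resolution within 14 days, and allows full dose for a non-DLT. If the event has not resolved by 14 days the subject should be withdrawn, with an exception: "However, if the investigator and GSK Medical Monitor agree that further treatment will benefit the subject, treatment can restart" one dose level lower under weekly monitoring.
- **Section 3.9.1.** "Approval from the GSK Medical Monitor is required to restart a dose after 14 days of dose interruption".
- **Section 8.3.1.1 and Appendix 3 (15.3.1, 15.3.2).** On any liver stopping event: "Immediately discontinue study treatment". Then: "If subject meets liver chemistry stopping criteria do not restart/rechallenge subject with study treatment unless" Medical Governance approval is granted, ethics approval is obtained if required, and "Separate consent for treatment restart/rechallenge is signed by the subject".
- **Section 6.3.** Treatment ends on "unacceptable toxicity, including meeting stopping criteria for liver chemistry defined in Section 8.3.1".

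**The concern.** ALT elevation is a known toxicity of this drug, and the protocol makes Table 4 one of the two rules for managing it. When the ALT rise also meets a liver stopping criterion, the two rules give different instructions for the same subject. Table 4 treats the event as a reversible toxicity with a routine dose reduction. Appendix 3 treats it as a reason to stop, with re-exposure exceptional and formally approved.

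What is at stake is subject safety, not an error rate or an estimate. Appendix 3 gives the reason for its safeguards: it cites 13% mortality on rechallenge after drug-induced liver injury across drugs. A site working from the Table 4 cell alone would bypass those safeguards while following a printed protocol instruction. Section 1.3.1 reports that the ALT rises so far improved once drug was withheld or discontinued. Withholding followed by improvement is exactly where the Table 4 restart pathway begins.

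**Working it through.** The protocol states no figure to reproduce. The check applies both rule sets to one event and counts what each requires before the next dose.

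**Event.** Drug-related ALT of 10×ULN, normal bilirubin, no symptoms, entry ALT ≤2.5×ULN, back to baseline on day 10.

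**Step 1: is it a liver stopping event?** Appendix 3 sets the absolute ALT criterion for this entry group at ≥5×ULN. Since 10 ≥ 5, it is.

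**Step 2: which Table 4 row applies?** The text shown does not print the CTCAE cut-offs for ALT. Assume the Grade 3 cut lies anywhere from 3×ULN to just under 10×ULN. Across that range the event is Grade 3 or 4, and both grades share one cell. The gap does not depend on this mapping, because no row of Table 4 has a liver exception and the Grade 2 row is more permissive still.

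**Step 3: count the approvals and consents named before restart.**

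| Rule | Instruction for this event | Named before restart |
|---|---|---|
| Section 3.8.3/Table 4, resolved within 14 days | Hold, then restart one level lower (full dose possible for a non-DLT) | 0 |
| Section 3.8.3 and Section 3.9.1, had it lasted beyond 14 days | Withdraw, or restart one level lower if the investigator and Medical Monitor agree | 1 (Medical Monitor) |
| Section 8.3.1.1/Appendix 3 | Stop at once; restart barred unless conditions are met | Medical Governance approval + separate signed consent = 2 fixed; ethics approval if required adds 1, so 2 to 3 |

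**Step 4: the other safeguards.** For a possibly drug-related event, Appendix 3 also limits rechallenge to subjects with compelling benefit and no effective alternative, at a dose set by the sponsor, with twice-weekly liver tests until stable. Table 4 has none of these.

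**Step 5: where the rules do not conflict.** Uncomplicated ALT ≥3 to <5×ULN, with entry ALT ≤2.5×ULN, may continue on treatment under the increased-monitoring part of Appendix 3, and management can satisfy both rules. The conflict is confined to events that meet a stopping criterion.

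**Step 6: does another section settle it?** Section 6.3 supports the liver rule. But Section 3.8.3 refers to Section 6.3 only for toxicity not resolved within 14 days, so a reader whose subject recovered on day 10 is not sent there. Section 6.3 also bars retreatment after permanent discontinuation, whereas Appendix 3 allows conditional rechallenge, so it does not explain how Table 4 and Appendix 3 fit together.

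**The case against.** The strongest reply is that this is an unstated precedence rather than a contradiction. Table 4 is labelled a guideline and the text below it is permissive, while Section 8.3.1.1 is a specific prohibition. A site can obey both by obtaining the approvals and consent first and then resuming at a reduced dose. The protocol handles other toxicities in the same layered way: QTcF prolongation and infusion reactions have their own sections, and Table 4 carves out neither. Any liver stopping event must be reported to the sponsor within 24 hours, so an unapproved restart would probably be noticed. The ALT rises reported so far came without bilirubin or INR increases, and all improved. Finally, only the second part of the protocol is shown, Section 3.8.3 is visible as amendment text, and an asterisk in Table 4 has no visible footnote.

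Much of this stands. Section 8.3.1 was probably meant to prevail, the reporting duty lowers the risk, and the absence of a carve-out can be asserted only for the text shown. Two points remain. The specific-over-general reading is weakened because Section 1.3.1 expressly applies Table 4 to liver toxicity, alongside Section 8.3.1 and without ranking them. And the Medical Monitor enters only after 14 days, which is neither the same body nor the same step as Medical Governance approval.

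**Conclusion.** The concern holds. For drug-related ALT events that meet a liver stopping criterion, Section 3.8.3/Table 4 leads to a less safe action than Section 8.3.1.1 and Appendix 3, and the protocol, as shown, does not tell a reader of Table 4 that its restart instruction does not apply. In the worked case the difference is 0 approvals or consents against 2 to 3, or 1 against 2 to 3 if the event lasts beyond 14 days.

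This rests on the Amendment 5 text of Section 3.8.3 and Table 4 and, for the grade of the worked case only, on the assumed CTCAE range. The number of subjects exposed to the conflict cannot be estimated, because the protocol gives no frequency or grade for the ALT rises. No endpoint, error rate or sample size is affected. It should be fixed because the toxicity is known and 2400 mg is still being explored.

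**What to change.** Make Section 8.3.1 and Appendix 3 the governing rule.

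- **Section 3.8.3/Table 4.** Add: *Events meeting the Section 8.3.1 liver stopping criteria are managed, and restart is decided, only under Section 8.3.1 and Appendix 3; Table 4 applies to liver events that do not meet those criteria.*
- **Section 1.3.1, Hepatic Toxicity row.** Add a clause that Section 8.3.1 takes precedence over Table 4.

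The cost is one sentence and one clause at the next amendment, with no new procedures, visits or subjects.

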**Section 3.2 Discussion of Study Design**

Rationale for Change – Updated to include expansion of any dose level during dose escalation to 12 subjects. At MTD, included Part 1 expansion cohort/analysis plan to include approximately 27 GCB-DLBCL subjects and approximately 15 subjects with solid tumors containing EZH2-sensitive mutations or prostate cancer to explore additional safety and preliminary efficacy. Updated in line with updates made through the protocol.

REVISED TEXT

After the accelerated dose titration, subjects will be enrolled in a standard 3+3 dose escalation design. Dose escalation will continue until a recommended Phase 2 dose (RP2D) is determined or until a maximum tolerated dose (MTD) or a dose of 3000 mg twice-weekly is reached ~~[Maximum Feasible Dose (MFD)]~~. After the RP2D (or MTD/MFD) has been determined in Part 1, then, Any dose level during Part 1 dose escalation may be expanded up to 12 subjects to explore safety and preliminary efficacy. At MTD/RP2D the cohort may be expanded to enroll approximately 27 GCB-DLBCL subjects and approximately 15 subjects with solid tumors containing EZH2-sensitive mutations or prostate cancer to explore additional safety and preliminary efficacy. Based on results of the Part 1 analysis in totality, Part 2 expansion cohorts may be opened. In Part 2, and subjects with will be assigned to one of four cohorts based on disease and EZH2 mutation status.

Safety assessments will be performed weekly for the first 4 weeks and then at regular intervals as outlined in the Time and Events Table (Section 7.1).

Disease response in lymphoma and solid tumor subjects will be assessed as described in the T&E table (Section 7.1).

Futility and Efficacy analysis will be performed on GCB-DLBCL subjects enrolled at the MTD/RP2D in cohort expansion of Part 1 as listed in Section 12.2.1.2.

Section 3.3.2 3+3 Dose Escalation Phase

Rationale for Change: Added definition of evaluable subject during dose escalation and moved text for PK/PD cohort to Part 2 of the study.

REVISED TEXT

An evaluable subject in Table 2 is defined as a subject who has been on study for at least 28 days (one cycle). Evaluation of safety data from at least 1 subject during the accelerated dose titration or at least 3 subjects in the standard dose titration who have completed 28 days of dosing on study (one cycle) is required prior to defining a new dose and starting the next cohort. Once a higher dose has been cleared, subjects at lower dose levels who remain on study drug and have not experienced dose limiting toxicity will be allowed to escalate up to that level.

Reverting from 3+3 Dose Escalation to Accelerated Dose Titration: Once Grade 2 toxicity is seen in one subject, there are 2 scenarios where the accelerated dose escalation may be resumed.

- 1) If two additional subjects are added at the dose where Grade 2 toxicity was seen in the initial subject and if no Grade 2 or higher toxicity is seen in either of the 2 new subjects, the accelerated dose escalation may be resumed, or
- 2) If the 3+3 method is used and, at the next higher dose, the 3 subjects do not have a grade 2 or higher toxicity, the accelerated dose escalation may be resumed.
(Before any decision is made to reinitiate accelerated dose titration a discussion between the investigators and the GSK medical monitor is required)

Part 1 PK/PD cohorts: Any dose level may be expanded up to 12 subjects in order to collect adequate data on safety, pharmacokinetics, or pharmacodynamics. Urine, bile, and additional blood samples may be collected following repeated administration for drug metabolite profiling and to obtain information on renal excretion of GSK2816126. Initially, optional pre- and post-treatment tumor biopsies will be requested. At MTD, mandatory collection of pre- and post-treatment tumor biopsies will be required for enrollment in a PK/PD cohort. Mandatory biopsies may be instituted at lower dose levels once evidence of target engagement has been demonstrated in surrogate tissue (e.g. H3K27me3 from PBMCs in blood); or if sufficient evidence of target engagement (e.g. dose dependence) is not observed in PD assay from surrogate tissue. Additional subjects may be enrolled at previously completed dose levels for the purpose of obtaining additional PK or PD data. A reduced PK schedule may be used in subjects enrolled to obtain additional PD data. These subjects may have the dose escalated to a higher completed dose level (not exceeding the MTD) once the necessary PK/PD procedures have been completed.

Section 3.3.5 Intra-subject Dose Escalation

Rationale for Change: Included additional text to clarify PK/PD and safety assessments for subjects who are approved for intra-subject dose escalation

REVISED TEXT

Decision on intra-subject dose escalation will be made after review of all safety data and approval by a GSK Medical Monitor and discussion with the investigator. In this case, the subject may begin dosing at the higher dose level as it will have already been demonstrated to be tolerable and monitoring will be performed as described in the protocol. Subjects approved for intra-subject dose escalation may require additional limited PK and/or PD sampling as determined by GSK Clinical Pharmacology. Additional safety assessments may be specified at the time of the dose escalation or schedule modification based on the safety profile in previous subjects at the higher dose level.

Section 3.3.7 Part 1: Futility and Efficacy Analysis for GCB-DLBCL Subjects

Rationale for Change: Text added to Section 3.3.7 and Section 3.4 include the patient populations to be enrolled in Part 1 expansion cohort and Part 2 and the statistical analysis that will be performed. GCB-DLBCL cohort expansion was added into Part 1 dose escalation phase. The study design was based on predictive probability methodology (Lee, 2008) to allow interim futility/efficacy assessment by comparing the overall responses with the pre-specified futility and efficacy stopping criteria, in order to enabling early decision of opening Part 2 expansion phase or terminating the trial. Additional details were moved to Section 12, Data Analysis and Statistical Considerations, of the protocol.

REVISED TEXT

There will be a GCB-DLBCL expansion cohort enrolled after the completion of dose escalation in Part 1. For the GCB-DLBCL expansion cohort in Part 1, futility and efficacy evaluation of overall response data will be performed in order to support the early decision regarding opening Part 2 dose expansion. The methodology is based on the Bayesian predictive probability of success if enrollment continues until all planned subjects are recruited [Lee, 2008]. Details of the predictive probability methodology, futility and efficacy evaluation are explained in Section 12.2.1.2. In summary, a minimum of 13 and maximum of 27 GCB-DLBCL patients will be enrolled. Once 13 GCB-DLBCL patients at MTD/RP2D have been enrolled (including patients in dose escalation phase) and have completed response assessments of safety and efficacy, response data will be reviewed on an ongoing basis for evidence of futility or efficacy.

For futility/efficacy analysis, subjects evaluable for response assessment will be defined by any or all of the following criteria:

- Subjects who have at least two post-baseline radiological disease assessments and have been on study for at least 28 days (one cycle.)

- Subjects who have progressed or have died or have withdrawn for study treatment due to any reason.

Interim analysis (IA) of futility and efficacy can be conducted at any time after 13 GCB-DLBCL subjects have enrolled and are evaluable for response assessment. If the thresholds for futility are met, the Part 1 expansion cohort may be stopped based upon the evaluation of the totality of the data. If the efficacy thresholds are reached, then Part 2 expansion may be opened. If neither futility nor efficacy thresholds are met at any interim analysis, and the totality of the data does not support continuation of the trial, then the trial may be terminated. All available data will be considered in making decision of termination or continuation of the trial.

Section 3.4 Part 2: Expansion Cohorts

Rationale for Change: Due to the improvement of response rates of cancer treatments over time, the study designs in Part 2 expansion phase based on predictive probability method were revised by updating the null and alternative hypothesis, to align with the current typical response rates. The sample size and futility stopping criteria for each cohort (GCB-DLBCL mutant and wild type, tFL mutant and wild type, and MM) are updated. Additional details were moved to Section 12, Data Analysis and Statistical Considerations, of the protocol.

REVISED TEXT

Part 2: Expansion Cohorts in both wild type and EZH2 mutation-positive GCB-DLBCL and tFL subjects, and subjects with MM

The primary objective of Part 2 is to investigate whether administration of GSK2816126 at the RP2D has a potentially clinically meaningful activity for more tumor types, if notable response rate is observed in Part 1 expansion cohort of GCB-DLBCL patients. Expansion cohorts will be enrolled in Part 2, including GCB-DLBCL and tFL patients with mutant and wild type EZH2 and patients with MM. Similar to Part 1 expansion design, Part 2 expansion design is planned based on predictive probability methodology. Rather than early stop for either futility or efficacy, Part 2 allows early stop for futility only. For each expansion cohort of GCB-DLBCL and tFL patients, a minimum of 10 and maximum of 32 patients will be enrolled at the RP2D. For MM cohort, a minimum of 14 and maximum of 40 patients will be enrolled at the RP2D. Interim analysis of response data will start from minimum number of patients enrolled and at any time thereafter. Details of Part 2 designs and stopping criteria are elaborated in Section 12.2. All available data will be considered in making decision of termination or continuation of the trial.

It is noted that patients with GCB-DLBCL, tFL and MM enrolled at MTD/RP2D in the previous stages of the trial (dose escalation and cohort expansion in Part 1) will be included for the Part 2 analysis.

Lymphoma subjects will be enrolled based on EZH2 mutation status. There will be up to 30 subjects per group in both GCB-DLBCL cohorts, up to 16 subjects per group in both tFL cohorts, and up to 37 subjects with MM. Multiple myeloma subjects will be selected independent of their EZH2 mutation status.

Further evaluation of futility:

The methodology is based on the predictive probability of success if enrollment continues until all planned subjects are recruited [Lee, 2008]. The predictive probability design is similar to a Green Dahlberg design in that it allows for early stopping for futility. The differences are that the predictive probability design allows for evaluation of stopping rules after each subject, rather than at only two stages, once a minimum number of subjects are evaluable. In this particular study, we will stop only for futility. While the two designs have similar type I and type II error rates, the probability of early termination is greater with the predictive probability design.

In both GCB-DLBCL mutation status cohorts, after, 12 subjects have been enrolled in each cohort to examine safety and efficacy, the number of observed confirmed responses will guide further enrollment according to the rules summarized in Figure 1. A maximum of 30 subjects per cohort will be enrolled at the RP2D. All available data will be considered in making enrollment decisions.

Figure 1 Diagram of Stopping Rules for GCB-DLBCL Cohort Expansion: GSK2816126

Number of Subjects	Number of Responses						
	0	1	2	3	4	5	≥6
12	Red						
13	Red						
14	Red	Red					
15	Red	Red					
16	Red	Red					
17	Red	Red					
18	Red	Red					
19	Red	Red					
20	Red	Red	Red				
21	Red	Red	Red				
22	Red	Red	Red				
23	Red	Red	Red				
24	Red	Red	Red	Red			
25	Red	Red	Red	Red			
26	Red	Red	Red	Red			
27	Red	Red	Red	Red			
28	Red	Red	Red	Red	Red		
29	Red	Red	Red	Red	Red		
30	Red	Red	Red	Red	Red	Red	

Figure 1 Legend: The shaded regions are the specific regions for stopping the study for futility. For instance, if there is only one response in fourteen subjects, then the predictive probability for success will be 5.0% or less (the futility criterion) and the study may be stopped.

In both tFL mutation status cohorts, after 12 subjects have been enrolled to examine safety and efficacy, the number of observed confirmed responses will guide further enrolment according to the rules summarized in Figure 2. A maximum of 16 subjects will be enrolled at the RP2D. All available data will be considered in making enrollment decisions.

Figure 2 Diagram of Stopping Rules for tFL Cohort Expansion: GSK2816126

Number of Subjects	Number of Responses			
	0	1	2	≥3
12				
13				
14				
15				
16				

Figure 2 Legend: The shaded regions are the specific regions for stopping the study for futility. For instance, if there is no response in twelve subjects, then the predictive probability for success will be 1% or less (the futility criterion) and the study may be stopped.

For the MM cohort: After 13 subjects have been enrolled to examine safety and efficacy, the number of observed confirmed responses will guide further enrollment according to the rules summarized in Figure 3. A maximum of 37 subjects will be enrolled at the RP2D. All available data will be considered in making enrollment decisions.

Figure 3 Diagram of Stopping Rules for MM Cohort Expansion

Number of Subjects	0	1	2	3	4
13					
14					
15					
16					
17					
18					
19					
20					
21					
22					
23					

Number of Subjects	0	1	2	3	4
24					
25					
26					
27					
28					
29					
30					
31					
32					
33					
34					
35					
36					
37					

The shaded regions are the specific regions for stopping the study for futility. For instance, if there is no response in 13 subjects, then the predictive probability for success will be 1% or less (the futility criterion) and the study may be stopped.

Section 3.4.1 Part 2 PK/PD cohort

Rationale for Change: Part 1 will focus on completion of the Part 1 expansion cohort. Potential to enroll subjects into a PK/PD cohort was moved to Part 2 of the study. Text was added to clarify that this cohort may be enrolled at the RP2D.

REVISED TEXT

In Part 2 a cohort of up to 12 subjects may be enrolled at RP2D to collect adequate data on safety, pharmacokinetics, or pharmacodynamics. Urine, bile, and additional blood samples may be collected following repeated administration for drug metabolite profiling and to obtain information on renal excretion of GSK2816126. Mandatory collection of pre- and post-treatment tumor biopsies will be required for enrollment in a PK/PD cohort.

Section 3.5.2 Rationale for Population

Rationale for Change: Included text to add Part 1 expansion cohorts of GCB-DLBCL and solid tumor subjects and rationale for inclusion of these tumor types.

REVISED TEXT

[figure not shown]
Therefore, the study includes subjects with nNon-Hodgkin's Lymphoma and enriched for subsets (GCB-DLBCL, tFL) as well as multiple myeloma and solid tumors that have relapsed or are refractory to prior treatment with standard of care or do not have standard of care available or refuse standard of care therapy.

Part 1 will be comprised of 2 phases:

- Part 1 dose escalation which will include subjects with MM, relapsed/refractory tFL andDLBCL, other NHLs and solid tumors , and
- Part 1 cohort expansion at the highest tolerated dose/MTD which will include a cohort ofsubjects with relapsed/refractory GCB-DLBCL and a cohort of subjects with prostate cancer or solid tumors containing EZH2 inhibition sensitizing mutations.

Part 2 will be comprised of cohort expansions in subjects with GCB-DLBCL, transformed follicular lymphoma and multiple myeloma.

EZH2 and H3K27me3 are dysregulated in nearly all cancers through numerous pathways including 1) recurrent gain-of-function heterozygous mutations in germinal center B-cell (GCB) DLBCL, FL, melanoma, and parathyroid adenoma, 2) EZH2 over-expression in numerous other aggressive tumors including those from prostate, breast, lung, liver, bladder, head and neck, skin, and kidney, and 3) inactivating mutations in UTX. H3K27 demethylase that acts in opposition to EZH2, described in numerous tumor types including transitional cell bladder carcinoma, esophageal squamous cell carcinoma, renal cell carcinoma, multiple myeloma, and subgroup 4 medulloblastoma (McCabe, 2014). Furthermore, data from prostate, breast, and several other tumor types have demonstrated that increased EZH2 expression correlates with increased aggressiveness of tumors and poor prognosis [GlaxoSmithKline Document Number 2013N169204_04, 2017]

McCabe 2014

Table 1. Tumor types harboring EZH2-activating mutations.

Tumor type	Tumor subtype	Mutated	Total	Frequency (%)	Mutations observed	Ref.
Lymphoma	NHL	33	127	26.0	1 A677G 1 A687V 31 Y641X	[28]
		4	25	16.0	Y641X	[32]
		5	35	14.3	Y641X	[33]
		5	41	12.2	1 A677G 4 Y641X	[12]
		31	320	9.7	Y641X	[13]
	GCB DLBCL	1	73	1.4	Y641X	[34]
		18	83	21.7	Y641X	[13]
		0	42	0.0	Y641X	[13]
	ABC DLBCL	101	366	27.6	7 A677G 5 A687V 50 Y641X	[26]
		12	55	21.8	Y641X	[33]
		9	60	15.0	Y641X	[32]
		26	221	11.8	Y641X	[10]
		18	251	7.2	Y641X	[13]
	Burkitt lymphoma	0	23	0.0	Y641X	[33]

With regard to haematological indications for GSK2816126, preclinical studies demonstrate that B-cell lymphomas of DLBCL with EZH2 activating mutations are the most sensitive to GSK2816126. Approximately 22% of GCB-DLBCL tumors have an EZH2-activating mutation, whereas ABC DLBCL does not contain EZH2- activating mutations (McCabe MT & Creasy 2014). Early follicular lymphoma lesions have been

shown to have EZH2 mutations, as well as mutations in other genes that disrupt chromatin structure [Friedberg Blood. 2015;125(1):40-47].

